This proposal unites neuroimagers, experts in conducting and analyzing human PET studies with behavioral scientists, experts in developing and testing treatments for alcoholism. We will conduct the first-ever *in vivo* PET imaging study of KOR and NTX occupancy in two cohorts of HD (18 FHP and 18 FHN) and relate our imaging findings to FH and alterations of drinking behavior by NTX in the ADP. Through this work, we will advance our understanding of (a) the degree of involvement of the kappa system in reducing drinking in humans by NTX, (b) the contribution of FH to this relationship, and (c) refine the use of a new PET imaging tracer. In so doing, we will inform the development of future targeted pharmacotherapies for alcoholism and lay the groundwork for other important investigations into the KOR/dynorphin system *in vivo*.

Primary (P), Secondary (S), and Auxiliary (A) Specific Aims:

- P1. **Occupancy of KOR by NTX and drinking:** To determine the degree to which occupancy of KORs by a 100 mg/day dose of NTX mediates (influences the strength of) responsivity to NTX treatment in all heavy drinkers. It is expected that KOR occupancy will significantly mediate the relationship between NTX treatment and responsivity. „Responsivity“, measured via ADP, is the change in number of drinks consumed at the baseline ADP vs. NTX ADP.
- P2. **Family History of Alcoholism as a moderator:** To determine whether the relationship between NTX responsivity and occupancy of KOR is different in FHP vs. FHN heavy drinkers.
- P3. To determine if baseline KOR availability differs between heavy drinkers and healthy control socialdrinkers

S1. **Baseline KOR differences**

- a. To determine if baseline levels of KOR differ between FHP and FHN heavy drinkers.
- b. To determine if baseline KOR level is related to either baseline drinking or responsivity to NTX.

S2. **Identify and validate a reference region** (area devoid of specific binding) for our new KOR tracer. A reference region would simplify PET analysis.

S3. **Optimize the scan duration** for clinical populations being imaged with the new KOR tracer.

Shorter scans would increase compliance and decrease discomfort to subjects.

A1. **Relationship to other behavioral measures:** To determine if occupancy of KORs is related to measures of alcohol craving, stimulation or sedation, assessed in the ADP.

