Our project will investigate a provocative finding in alcohol treatment research [3]. Namely, that FH of alcoholism may influence (or be a marker of an underlying trait that influences) the response of heavy drinkers (HD) to NTX. Simply put, not every HD responds favorably to NTX but lower levels of drinking can be achieved and risk of relapse is diminished in some. It is essential for clinical treatment and future drug development to understand how NTX works. Preclinical results have implicated kappa in *changes* in alcohol drinking, but the directionality of these changes are complex. We propose that the differential efficacy of naltrexone may be related to differences in occupancy of kappa opioid receptors by naltrexone. This translational project will test this hypothesis. The results of this project could not only help maximize treatment effectiveness of naltrexone but also result in identification of new medication treatment targets for more optimal reduction of alcohol drinking.

3. Research Plan: Provide an orderly scientific description of the study design and research procedures as they directly affect the subjects.

A total of 56 HD subjects will be tested; equal numbers of FHP and FHN subjects will be recruited. Data from the first year's subjects ("initial cohort" perhaps specify how many will be used for this purpose) will be analyzed prior to scanning the remaining subjects in order to address aims S2 and S3 (identification and validation of a reference region; reduction in scan duration) which are addressed below in PET methods.

Study design: Because we are interested in investigating the implications of baseline KOR, as well as Occupancy of KOR by NTX, we must perform 2 PET scans on each subject; one at

baseline and one following 5-11 days of NTX pretreatment. Similarly, because we are interested in relating responsivity to occupancy of KOR by NTX we must make two assessments of drinking behavior using the ADP; one at baseline the day before or after the first PET scan and one following 5-11 days of treatment with NTX. The post PET scan and post ADP will ideally take place on Day 6 or Day 7 of medication, but we will allow up to 11 days of medication for scheduling issues and the possibility that the appointments will be within this time frame. All

In designing the study, we had to balance various competing interests and we provide justifications below:

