PK samples: Two PK samples will be collected during the NTX PET session. Days 5-11 were chosen for the NTX PET scan to build some flexibility into scheduling but maximize the likelihood that NTX levels would be at equilibrium, which will be confirmed by PK analyses. We will also look (on a population basis) for a relationship between occupancy of KOR and NTX (and 6(beta)-naltrexol) levels and interaction with FH of alcoholism.

ROI analysis and parametric image generation: After data reconstruction with all corrections, a new summed image (0-10 min) will be registered to the subject’s T1-weighted MR image, which will be registered to an MR template so that PET and MR images are in the same MNI space. ROI’s, including the 13 examined in the Preliminary data section in Figures 4 and 6 will be taken from a template (Anatomical Automatic Labeling (AAL) for SPM2).

Possible to dispense with arterial sampling, 2T model fitting?: Preliminary results suggest that the

cerebellum may be an appropriate reference region. That is, it may be devoid of KOR. It certainly has low specific binding compared to the other regions assayed. The excellent agreement between BP_{ND} estimated by the 2T model and by SRTM certainly suggests that in healthy controls, we can assess BP_{ND} at baseline with a reference region model using the cerebellum as the reference region. If this turns out to be generally true (e.g., in larger samples, in heavy drinkers), then we can justifiably dispense with arterial sampling and analyze all data via reference tissue models (such as SRTM and SRTM2). As mentioned in Preliminary PET studies, to validate the absence of KOR in the cerebellum, under multiple scan conditions (baseline and NTX) in clinical populations, we will have to show that V_T of cerebellum does not change between baseline and NTX (i.e., there is no specific binding to block).

Possible to shorten scan duration?:

Preliminary results also indicate that we could shorten the scan duration from 2 hrs (used in our preliminary scans) to 1 ½ hrs without any loss of accuracy or precision.

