Analysis of Initial Cohort: Data from the first 6 FHP and 6 FHN subjects scanned in year one of the project (24 scans total) will be analyzed to determine whether or not a reference region exists for [11C]LY2795050 ([11C]-PKAB) and whether or not the scan duration can be shortened without loss of precision of the data. To be sure that a reference tissue model is appropriate in our study, two findings are required. The V_T of the putative reference region must be unchanged by blocking and the endpoint, BP_{ND} , estimated by the reference region method must agree with the BP_{ND} calculated using an AIF. If the BP_{ND} values from 2T and SRTM continue to show excellent agreement, as applied to *both* baseline and NTX scans, then we may choose to discontinue arterial sampling thereafter and rely solely on a reference region model for analysis. After a preliminary analysis of the initial cohort, we will determine the acquisition protocol for the remaining 24 subjects.

Modeling of PET data to yield BP in regions of interest and parametric images

1. Standard kinetic modeling approaches: With plasma input function measurements in hand, we can compare multiple standard methods of estimating our desired endpoints (BP_{ND} at baseline and difference in BP_{ND} from baseline to NTX) to determine the best model or technique [52] that yields the lowest variance in the estimates. Tentatively based on preliminary data, we expect to use the cerebellum as the reference region for reference region methods but we will continue to investigate the possibility of another (better) reference region.

2. Measuring occupancy does not depend on displacement, time of day:

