Primary Aim 1. Occupancy of KOR by NTX and drinking. This aim seeks to determine the degree to which occupancy of kappa by NTX mediates responsivity to NTX in heavy drinkers. Responsivity to NTX is defined as the change in the total number of drinks consumed in the NTX ADP versus the baseline ADP. Tests for mediation will be conducted using the regression strategies described initially Baron and Kenny [53], and the more recent elaboration by Kraemer et al. [54]. The proposed mediator (i.e., the potential mechanism of change), occupancy of KORs, is measured as the fractional change in BP_{ND} before and after treatment with NTX. The analyses will determine whether occupancy is associated with a) NTX treatment, and b) NTX responsivity.

Primary Aim 2. Family History of Alcoholism as a moderator: This aim seeks to determine if the relationship between NTX responsivity and occupancy of KOR is altered by FH status. FHP and FHN will be compared on NTX responsivity and occupancy of KOR. Tests for moderation will be conducted using the strategies described by Baron and Kenny [53], and the elaborated by Kraemer et al. [54]. The primary tests will be whether there is a significant FH by dose interaction on NTX response and occupancy of KOR.

Secondary Aim 1. Baseline KOR differences. This aim seeks to determine if baseline levels of KOR differ between FHP and FHN heavy drinkers, and are related to either drinking in baseline or NTX ADP. FHP and FHN groups will be compared using chi-square tests for categorical variables, and using t-tests or Mann-Whitney tests for continuous variables. All continuous variables will be examined for adherence to the normal distribution using normal probability plots and Kolmogorov-Smirnov tests. If normality is not satisfied and transformations do not help with achieving normality, alternative analytic strategies will be considered such as generalized estimating equations or nonparametric methods. The relationship between baseline KOR and drinking will be examined via Pearson product-moment correlations.

Secondary Aims 2 and 3. Scan duration and reference region. We will look for correlations between BP_{ND} estimates based on 2T model with full AIF and all data vs alternative models and data ranges. Group variances in baseline KOR at or lower than 2T estimates will permit adoption of simpler models.

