region. However, the definitive identification of a reference region must be based on displacement experiments.

f. Regional distribution of desired endpoint: KOR at baseline (BP_{ND})

We computed BP_{ND} in each ROI two ways. One method requires the use of AIF and the other does not. From the fits of the TAC data via 2T model with AIF, we calculated BP_{ND} as the relative difference in volumes of distribution between the target ROI and the putative reference region, in this case, cerebellum: $(V_T(ROI) - V_T(CER)) / V_T(CER)$. BP_{ND} was also computed using the Simplified Reference Tissue Model (SRTM) using the cerebellum as the reference region. The regional distribution of BP_{ND} based on 2T and SRTM is shown in Figure 4. Figure 4 shows that the methods are in close agreement and the variability, by region, across the cohort is small.

[figure not shown]

Figure 5 **a.** Effect of pre-block with unlabeled KOR antagonist drug. Baseline TACs for cerebellum (CER), caudate (CAU), and frontal cortex (FRO) (solid circles, open circles, diamond, all in red). Curves after pre-block (blue) all show reduced specific binding and are nearly indistinguishable from CER at baseline. Curves are from one animal and are normalized to injected activity dose. **b.** BP_{ND} is reduced dose-dependently according to dose of specific KOR antagonist in both CAU and FRO region.

g. Pre-blocking of [11C]LY2795050 ([C-11]-PKAB): can we detect drug occupancy at kappa sites?

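### The statistical section lets a simpler PET model be adopted on correlation and baseline variance alone, a rule that cannot see a constant shift, rewards shrunken estimates and omits the findings PET Methods requires

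*Combined protocol and SAP*

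**What the plan says.** Two places govern when simpler PET modelling may be adopted.

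- **Statistical Considerations, Secondary Aims 2 and 3.** BP_ND from the 2T model with full arterial input and all data is to be correlated with BP_ND from alternative models and data ranges. The decision sentence follows: "Group variances in baseline KOR at or lower than 2T estimates will permit adoption of simpler models". No minimum correlation, bias limit, V_T condition or NTX-scan condition is given.
- **PET Methods, Analysis of Initial Cohort.** For a reference tissue model, "two findings are required": V_T of the reference region unchanged by blocking, and reference-method BP_ND agreeing with the arterial-input BP_ND. The stopping sentence says that if 2T and SRTM agree on both baseline and NTX scans, "then we may choose to discontinue arterial sampling thereafter and rely solely on a reference region model for analysis". That sentence does not repeat the V_T condition.

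Other relevant text:

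- The Research Plan introduces aims S2 and S3 as ones "which are addressed below in PET methods".
- PET Methods, on dispensing with arterial sampling: "we will have to show that V_T of cerebellum does not change between baseline and NTX". Section VI, item h, repeats this as the condition for validation.
- Specific Aim S2 is to "Identify and validate a reference region".
- The kinetic-modelling paragraph of PET Methods seeks the technique that "yields the lowest variance in the estimates".

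**The concern.** The statistical section words its variance condition as sufficient, and that condition does not measure whether the simpler model gives the right answer. Correlation and between-person variance are both unaffected by a constant error. Group variance also mixes true differences between people with measurement error, so a lower value does not show better precision and can simply reflect compressed estimates.

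The V_T check matters for a separate reason. Section VI, item f, computes the 2T BP_ND as the "relative difference in volumes of distribution between the target ROI and the putative reference region, in this case, cerebellum". The 2T and SRTM estimates therefore share the cerebellum, and their agreement cannot reveal specific binding there. Section VI, item h, acknowledges that agreement does not validate the region.

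At stake is occupancy, the fractional change in BP_ND, which is the mediator in P1 and enters P2. Baseline KOR, the endpoint of P3 and S1, is affected to a lesser degree. Once arterial sampling stops, V_T cannot be measured in later heavy drinkers: 24 according to Analysis of Initial Cohort, or 56 - 12 = 44 under the Research Plan total. Any correction would then rest on the average from the first 12.

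**Working it through.** The rule has no stated operating figure to reproduce. The first step is algebra. The later steps use assumed inputs, because the documents give no group means or SDs for BP_ND.

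**1. Algebra (no assumptions).** Let the simpler model return y = a + b·x, where x is the 2T value and b > 0. Then corr(x, y) = 1 and Var(y) = b²·Var(x).
- Pure shift (b = 1): the variance ratio is 1 whatever the size of a.
- Scaling by 0.9: ratio 0.81. Scaling by 1.1: ratio 1.21.

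**2. How often the variance condition passes.** Assumed: mean BP_ND 0.8; n = 12 (6 FHP and 6 FHN, from Analysis of Initial Cohort); between-subject SD 0.08–0.24; independent, equal measurement SD 0.02–0.05; 40,000 simulated cohorts per cell.

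| Simpler model | Passes, over the range | Passes at SD 0.16, error 0.03 |
|---|---|---|
| No fault | about 50% | 50% |
| Shift -0.1 or +0.1 | about 50% | about 50% |
| Scaled by 0.9 | 63–99% | 88% |
| Scaled by 1.1 | 1–37% | 12% |

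In the base case the median correlation is 0.96–0.97 throughout, so the correlation does not separate these models.

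**3. The preliminary fit (indicative only).** Section VI, item h, reports SRTM = 1.01 × 2T with R² = 0.98 and treats this as excellent agreement. Read as a least-squares fit, Var(SRTM)/Var(2T) = 1.01²/0.98 = 1.0201/0.98 = 1.04, which misses the condition. Cohorts of 12 with that slope and R² pass 32% of the time. The fit pools regions and prints no intercept, so it is not a group variance in the sense of the rule.

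**4. Effect of a shift on occupancy.** With shift s in both scans, apparent occupancy = B·occ/(B + s). For B = 0.8 and true occupancy 60%, the numerator is 0.48:
- s = -0.1: 0.48/0.70 = 68.6%
- s = -0.05: 0.48/0.75 = 64.0%
- s = +0.1: 0.48/0.90 = 53.3%

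If FHP baseline were 0.7 and FHN 0.8 (the direction hypothesised in the protocol; values assumed), s = -0.1 gives 0.42/0.60 = 70.0% against 68.6%, a spurious difference of 1.4 points. Equal scaling cancels: (kB - kB(1 - occ))/(kB) = occ.

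**5. Cerebellar binding c.** Apparent BP_ND = (B - c)/(1 + c). On NTX, B and c are each multiplied by (1 - occ). The V_T change is (1 + c(1 - occ))/(1 + c) - 1.
- c = 0.05: baseline 0.75/1.05 = 0.714, a bias of -10.7%; 60% occupancy reads 58.8%.
- c = 0.1: baseline 0.70/1.10 = 0.636, a bias of -20.5%; NTX 0.28/1.04 = 0.269; 60% occupancy reads 57.7%. V_T changes by 1.04/1.10 - 1 = -5.5%.

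With c = 0.1 or 0.2 the variance condition still passes about 50% of the time.

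**6. What 12 participants can show about V_T.** The 95% half-width is t(11) × SD/√12: 2.201 × 5/3.464 = 3.2 points if the SD of change is 5%, and 6.4 points if it is 10%. With an observed change of zero at 60% occupancy, those intervals still allow BP_ND bias up to -12% and -24%, with 60% occupancy reading 58.7% and 57.3%. A two-sided 0.05 test would find no significant change with c = 0.1 in 7%, 59% and 79% of cohorts at SD 5%, 10% and 15%. A non-significant result alone is therefore weak evidence that V_T is unchanged.

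**The case against.** The strongest reply is that the plan already contains the right test. The Research Plan sends S2 and S3 to PET Methods, which demands both findings, and the V_T condition appears in three places. On this view the statistical section is a short summary, and permitting adoption can be read as one condition among others. Applied together with PET Methods, the variance condition is an extra hurdle, not a weaker one. This stands in part: harm needs the statistical section to be applied in place of PET Methods. But its sentence is worded as sufficient. The PET Methods stopping sentence itself rests on BP_ND agreement without V_T, and its model-selection sentence also favours lowest variance.

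Other points:

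- **The shift is hypothetical.** True. Nothing in the documents suggests one, and the preliminary agreement was close. That evidence comes from seven healthy volunteers without NTX.
- **Test/retest was slightly better for SRTM.** The indices are 7.2% against 8.2%. Giving SRTM 12% lower error (1 - 7.2/8.2 = 0.12) moves the no-fault pass rate only to 51–56%.
- **Cerebellar binding would also bias the 2T result.** True. The switch does not cause it. The document's evidence on binding is reassuring but limited: blocking curves from one animal, which the protocol does not treat as proof.
- **Scan duration.** V_T has no bearing on S3. The preliminary 90- and 120-minute results were nearly the same, so only a bias and agreement check is missing there.

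**Conclusion.** The concern holds. The statistical section states a rule different from the one in PET Methods. Taken by itself, that rule is the weaker of the two for adopting a reference-region model, and it does not target bias. Its blindness to a shift and its preference for shrinkage follow from algebra alone. The pass rates and occupancy figures rest on assumed BP_ND, SDs, shifts and occupancy.

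The consequences are limited:

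- A shift specific to the simpler model biases occupancy (60% reads between 53.3% and 68.6% for shifts of ±0.1).
- Scaling that is equal in both scans cancels in occupancy.
- A shift or scaling common to everyone leaves the P3 and S1 group tests unchanged.
- Cerebellar binding biases absolute BP_ND, and occupancy only modestly. It distorts the P3 and S1 tests only if it differs between people or groups.

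The text should be corrected before the initial cohort is analysed, because V_T cannot be recovered for participants scanned without arterial sampling.

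**What to change.** In Statistical Considerations, Secondary Aims 2 and 3, replace the variance rule with the two PET Methods findings for a reference-region model:

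1. Cerebellar V_T unchanged from baseline to NTX. Report the paired mean change with its confidence interval, and the BP_ND and occupancy bias that interval allows, rather than a non-significant test alone.
2. Mean bias and limits of agreement for BP_ND and occupancy against 2T with arterial input, on both baseline and NTX scans.

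Repeat the V_T condition in the PET Methods stopping sentence. For shorter scans, require only the bias and agreement check against the 120-minute data. In both sections, use variance only to choose among models that have passed. The sponsor should set the margins in advance.

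The direct cost is wording and some added analysis of the 24 scans already planned. The real cost is that arterial sampling or longer scans continue if the findings are not met, and the margin drives how often that happens. Take a margin as met when the 90% confidence interval lies inside it, with 12 participants:

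| Margin | True state | SD of change 5% | SD of change 10% |
|---|---|---|---|
| 5% | valid region | met in 89% | met in 11% |
| 10% | valid region | met in 100% | met in 89% |
| 10% | binding of 0.1, 60% occupancy | met in 90% | met in 43% |

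A tight margin may often reject a valid region, and a loose one may often accept an invalid one. That trade-off is the sponsor's to make.

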- l) Psychophysiological Measures: These will include heart rate and blood pressure monitored

using a Critikon Dinamap while skin temperature will be measured using Yellow Springs Instruments 4600 precision thermometer. The cuff of the Dinamap will be on the subject's dominant arm while the probe of will be attached to the middle finger of the subject's non-dominant arm. These data will be further used to examine the safety of using the medication combination during alcohol self-administration.

1) **Cold Pressor Task** (Edens & Gil, 1995): To evaluate the ability of participants to deal with a physiological stressor and to examine pain thresholds in relation to medication effects and drinking behavior. Subjects will be informed that the experimenters are investigating the body's physiological response to cold water during nicotine withdrawal. Subjects will be asked to immerse their right arms into ice water maintained at 3-4°C. Subjects are asked to raise their left hand when they begin to feel pain (pain threshold) and to remove their hand from the water when they can no longer tolerate the pain (pain tolerance). While their hand is immersed in water subjects are also asked to rate their pain on an analog scale of 0-100.

3. **Statistical Considerations:** Describe the statistical analyses that support the study design. Outcomes for this study will be collected using scannable forms (Teleforms). The scanned forms will be processed through the Teleforms software and exported to a database on a secure computer. Error checking and data validation will occur weekly and any problems will be queried and resolved immediately. Drs. [name] will receive monthly data quality reports to check for completeness and accuracy of key demographic and prognostic variables, as well as rates of recruitment, retention, and follow-up. Statistical tests will be conducted using SAS v9.1 and SPSS v16 (or later) and will be performed at 2-tailed alpha level of 0.05

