Auxiliary Aim 1. Kappa and behavioral indicators relevant for alcoholism. This aim will examine the correlations between occupancy of KOR and alcohol craving, stimulation and sedation. A series of Spearman rank-order and Pearson correlation analyses will be conducted for this aim.

Power analysis: The sample size was based on the power calculations for the hypotheses of (a) reduced drinking in the NTX 100 condition, and (b) power to detect an interaction by FH. Power calculations were generated using G*Power software Version 3.0 [55]. Effect sizes were estimated based on the preliminary FH and NTX effects on drinking behavior in the ADP described in [6] and in our preliminary studies. The effect size for the effect of FH is .91. To detect this effect size at $\alpha=.05$ with 80% power, a total of 16 participants would be required for each arm. Therefore the proposed sample size of $n=18$ per arm would be sufficient to detect differences in drinking between FHP and FHN at the 100 mg dose of naltrexone.

SECTION VI: RESEARCH INVOLVING DRUGS, DEVICES, BIOLOGICS & PLACEBOS

Are there any investigational devices used or investigational procedures performed in a YNHH Operating Room? Yes No *If Yes, please be aware of the following requirements:*

- a. A YNHH OR New Product/Trial Request Form must be completed. Please contact the OR Materials Manager, [name], at [contact] for more information on this requirement;
- b. Your request must be reviewed and approved by the Operating Room New Technology Committee before patients may be scheduled; and
- c. The notice of approval from the OR New Technology Committee must be submitted to the HIC for the protocol file.

1. **Identification of Drug, Device or Biologic:** What is (are) the **name(s)** of the drug(s), device(s) or biologic(s) being used? Identify whether FDA approval has been granted and for what indication(s).
Naltrexone is an FDA approved drug that is used in the treatment of alcoholism and opioid addiction.
[C-11]LY2795050 ([C-11]PKAB) PET radiotracer to image kappa opioid receptor, Production of [C-11]LY2795050 ([C-11]PKAB) will be performed with the permission of Yale-New Haven Hospital RDRC

All protocols which utilize a drug, device or biologic **not** approved by, but regulated by, the FDA must provide the following information: **Not applicable to this research project**

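### The power paragraph claims power for an FH interaction but shows only one FHP–FHN contrast, and its 16 per arm gives 80% power only one-sided, against the plan's two-tailed 0.05

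*Combined protocol and SAP*

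**What the plan says.** All of the sizing is in the Power analysis paragraph of Statistical Considerations. It names two hypotheses as the basis for the sample size: reduced drinking on naltrexone 100 mg, and "b) power to detect an interaction by FH". One calculation follows. Its input is "The effect size for the effect of FH is .91" and its result is that, at alpha .05, "with 80% power, a total of 16 participants would be required for each arm". The planned 18 per arm is then called "sufficient to detect differences in drinking between FHP and FHN at the 100 mg dose of naltrexone". The sidedness of alpha, the test, and the metric of .91 are not given there. Earlier in the same section, all tests "will be performed at 2-tailed alpha level of 0.05".

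Primary Aim 2 is described in two ways. The Specific Aims give it as "To determine whether the relationship between NTX responsivity and occupancy of KOR is different in FHP vs. FHN heavy drinkers", which is a difference in slopes, and the Primary Aim 2 analysis paragraph opens in the same terms. That paragraph then names FH-by-dose interactions, on response and on occupancy, as the primary tests. The outcome is a change score: "Responsivity to NTX is defined as the change in the total number of drinks consumed in the NTX ADP versus the baseline ADP".

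The group size also varies. The introduction to the Specific Aims and the power paragraph use 18 per FH group. The initial-cohort plan agrees, with 12 subjects followed by a remaining 24, or 36 in all. Targeted Enrollment, the Research Plan, Recruitment Procedures and Subject Population give 56 heavy drinkers, which is 28 per group if equal.

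**The concern.** The paragraph promises power for an interaction and closes on a between-group difference at one dose. These are different quantities. The conclusion as worded contains no baseline session and no occupancy term. No interaction effect, slope, occupancy SD or between-session correlation is given anywhere, so the 80% cannot be carried over to Aim 2.

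The number itself is also in doubt, because an effect of .91 with 16 per arm does not look like a two-sided result. FH moderation is a primary aim, and a reader would reasonably take 18 per arm to be adequate for it on the strength of this paragraph.

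**Working it through.** **Inputs from the plan.** Effect .91 (read as Cohen's d, since no metric is named), alpha .05, target power 80%, 16 required and 18 planned per arm, two-tailed tests, and 28 per arm from the 56-subject target.

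**Step 1. Reproduce the 16.** For two independent means, the normal approximation is n per arm = 2[(z_alpha + z_power)/d]².
- One-sided: 2[(1.645 + 0.842)/.91]² = 14.9, so 15. The exact noncentral t gives 16.
- Two-sided: 2[(1.960 + 0.842)/.91]² = 19.0, so 19. The exact noncentral t gives 20.

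The stated 16 therefore matches only the one-sided t-test. A Mann-Whitney version (relative efficiency 0.955) gives about 17 one-sided and 21 two-sided. A paired or one-sample t-test needs only about 9 or 12 subjects in total.

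**Step 2. Power at the plan's two-tailed 0.05.** Noncentral t with df = 2n − 2 and noncentrality d·√(n/2).

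| n per arm | Noncentrality | Two-sided | One-sided |
|---|---|---|---|
| 16 | .91·√8 = 2.57 | 70.2% | 80.8% |
| 18 | .91·√9 = 2.73 | 75.6% | 84.9% |
| 28 | .91·√14 = 3.40 | 91.7% | 95.7% |

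**Step 3. FH-by-dose test on drinks.** With two sessions, this is a two-group t-test of change in drinks. If .91 is already on the change scale, Step 2 applies unaltered. If .91 is in single-session SDs, and baseline means and session SDs are equal, the SD of change is σ√(2(1 − ρ)), so d for change = .91/√(2(1 − ρ)). The plan does not give the session correlation ρ, so the values below are assumptions. Power is two-sided.

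| ρ | d for change | 18 per arm | 28 per arm |
|---|---|---|---|
| 0 | .64 | 47% | 66% |
| .3 | .77 | 61% | 81% |
| .5 | .91 | 76% | 92% |
| .6 | 1.02 | 84% | 96% |
| .7 | 1.18 | 93% | 99% |

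**Step 4. Occupancy-by-FH term.** The plan gives no effect size, so the useful figure is the detectable difference. Compare two correlations by Fisher z, with SE = √(2/(n − 3)). This equals a slope comparison only if the SD ratio of responsivity to occupancy is the same in both FH groups.
- 18 per arm: 2.802·√(2/15) = 1.023 on the z scale, which is r = .47 vs −.47, or .77 vs 0.
- 28 per arm: 2.802·√(2/25) = 0.792, which is r = .38 vs −.38.

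**Illustration only.** Converting d to r gives .91/√(.91² + 4) = .41. At 18 per arm, .41 vs 0 has 22.6% power and .41 vs −.41 has 67.4%; simulating the regression interaction gives 22.0% and 68.4%. At 28 per arm the Fisher figures are 34.4% and 87.6%. Other readings of .91 at 18 per arm give other answers:
- Partial f² = (.91/2)² = .207: 75.4%.
- Standardised slope difference of .91 with residual SD 1: about 69%.
- Slopes of ±.455 with total variance 1: 78%.
- Slopes of .91 and 0 with total variance 1: 88%.

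**The case against.** The strongest reply is that the interaction in the power paragraph is the FH-by-dose interaction named as a primary test for Aim 2. For drinks, that test is a two-group t-test of change scores. The effect sizes are said to come from earlier FH and naltrexone effects in the drinking paradigm, so .91 may already be a change-scale effect, and then the form of the calculation is right. This stands as a possibility. The phrase about drinking at the 100 mg dose leans towards a single session but does not settle the scale, and the t-test itself is an inference from the match at 16. Even on this reading, two-sided power at 18 is 75.6%, and neither the slope difference nor an FH difference in occupancy is covered.

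It is also fair that 28 per arm would give more than 80% for .91 read as d. But the power paragraph argues from 18.

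A reader might infer that Aim 2 has only about 22–68% power. The documents do not support that. A mean FH difference in drinks says nothing about an occupancy slope, and the range comes from a d-to-r conversion and slope patterns that are not in the plan. Nor do they support saying that the drinks interaction cannot reach 80%: at 18 per arm it does so once the session correlation is somewhere between .5 and .6. The plan also nowhere says that it would read a null interaction as absence of moderation, and its design rationale speaks only of finding an initial signal.

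**Conclusion.** The paragraph is wrong as written, on two counts. First, it claims power for an FH interaction but shows none for the occupancy-by-FH slope difference or for FH differences in occupancy. It reaches the drinks interaction only if .91 is a change-scale effect. Second, its 80% at 16 per arm is a one-sided result under a two-tailed plan. The two-sided requirement is 20 per arm, with 70.2% at 16, 75.6% at 18 and 91.7% at 28.

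The second count assumes that .91 is Cohen's d in a two-sample t-test, which the exact one-sided match supports. The actual power for Aim 2 cannot be determined from the documents. The figures in Steps 3 and 4 are conditional ranges and should be labelled as such. This should be corrected, but it does not invalidate the design.

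**What to change.** In the Power analysis paragraph:
- Restate the calculation at two-sided 0.05: 20 per arm for 80%, with 75.6% at 18 or 91.7% at 28.
- Reconcile 18 per arm with the 56 heavy drinkers given elsewhere, and use one n throughout.
- State the metric of .91, and whether it is on drinks at 100 mg or on change from baseline. Limit the power claim to that contrast.
- For Aim 2, replace the implied 80% with assumption-labelled figures: the power of the change-in-drinks test over a range of session correlations, and the detectable occupancy-by-FH difference (about r = .47 vs −.47 at 18 per arm, .38 vs −.38 at 28) with its equal-SD-ratio condition. If the 22–68% range (34–88% at 28) is shown at all, mark it as an illustration.

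In the Primary Aim 2 paragraph, say how the slope question and the FH-by-dose tests relate, and report the interaction with a 95% confidence interval.

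The cost is rewording these paragraphs and aligning the sample-size statements. No participants or procedures are added. The downside is that the stated power looks less favourable.
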